4.3.1 Rationale for Dose Selection/Regimen/Modification

Mosunetuzumab

Mosunetuzumab monotherapy has been examined in relapsed/refractory B-cell NHL⁶ as well as untreated DLBCL in patients unfit for standard treatment²¹.

Subcutaneous mosunetuzumab has been tested in a phase 1/1b with both flat dosing as well as step-up dosing [Matasar, 2020 #1294]. In the flat dosing cohort, patients were treated at 1.6 to 20 mg dose cohorts in a standard 3+3 design. A single DLT was observed at 1.6 mg (grade 4 neutropenia). Escalation otherwise proceeded without any other DLTs observed in other cohorts, and 26 patients treated at the final 20 mg dose. All CRS events across all cohorts were grade 1 (n=6, 26%) and grade 2 (n=2, 9%) and occurred during cycle 1. Efficacy in relapsed/refractory indolent NHL

patients were similar to results seen in the previously presented intravenous cohorts.

To further reduce the rate and severity of CRS events, and to improve patient convenience, mosunetuzumab SC step-up dosing regimens of 5/15/45 mg (F1) and 5/45/45 mg (F2) are being evaluated in Study GO29781 Group F. The C1D1 dose of 5 mg SC was selected as the projected C_{max} is similar to 1 mg IV, the recommended initial dose of the IV step-up dosing regimen. This starting dose of 5 mg was within the range evaluated in the Group D flat dosing schedule. The target dose was selected at 45 mg SC, as it is projected to provide a lower C_{max} (population pharmacokinetics [popPK] model predicted geometric mean ratio [GMR] = 0.37) but higher AUC ([GMR] = 1.49) at steady state than the 30 mg IV maintenance dose. Therefore, it is expected to be associated with sufficient exposure to drive anti-tumor activity with a potentially lower risk of CRS compared with Mosunetuzumab IV 1/2/60/30 mg dosing. Two different doses (15 mg and 45 mg) were evaluated on C1D8 to further evaluate step-up dosing for CRS mitigation to reach the target dose of 45 mg. The 5/45/45 mg dosing regimen showed comparable safety profiles to the 5/15/45 mg dosing regimen but with a shortened window of CRS associated mostly with only the first two doses of mosunetuzumab during cycle 1. Further, the 5/45/45 mg dosing regimen also allows faster achievement of target dose. Therefore, this dose is considered the preferred dose for mosunetuzumab SC monotherapy.

Polatuzumab vedotin combinations in B-cell NHL

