5.3 Study Treatments

For the purposes of this protocol, Part A will refer to the subcutaneous (SC) mosunetuzumab monotherapy portion, while part B will refer to the polatuzumab vedotin and obinutuzumab combination portion.

Part A

The dosing of SC mosunetuzumab is listed in Table 2. Cycle length is 21 days. The rationale for this dosing is described in section 4.2.1. A step-up regimen will be employed to minimize the risk of CRS. Subjects will receive lower doses of the drug on cycle 1 day 1 and achieving the full dose on cycle 1 day 8. The full dose alone will be given on cycle 2 through 8 on day 1 only.

Table 2: SC mosunetuzumab dosing

	Cycle 1			Cycle 2-8
	Day 1	Day 8	Day 15	Day 1
Mosunetuzumab dose (SC)	5 mg	45 mg	45 mg	45 mg

Cycle length = 21 days

Subcutaneous mosunetuzumab will be prepared and administered according to appendix 14.15. Corticosteroids (dexamethasone 10 mg PO or equivalent) should be given pre-dose as well as 24 hours (+/- 4 hours) and 48 hours (+/- 4 hours) post dose during cycles 1 and 2. Oral acetaminophen (500-1000 mg) and/or diphenhydramine (25-50 mg) may also be administered per standard institutional practice prior to mosunetuzumab. Pre-medications from cycle 3 onward are optional provided that the patient did not have cytokine release syndrome during the previous cycle. Hydration and tumor lysis syndrome (TLS) prophylaxis is also at the discretion of the investigator. Corticosteroid administration in cycle 3 and beyond is up to the investigator. However, if a subject experiences CRS then corticosteroids should be administered for the subsequent doses until no CRS is observed.

For SC administration, mosunetuzumab will be administered by qualified staff over 30 seconds to 2 minutes. Refer to appendix 14.15 for more details including syringe size and preferred injection site. The recommended management of injection-site reactions is detailed in Appendix 14.14

Following each mosunetuzumab dose, patients will be observed at least 30 minutes for cycle 1 day 1 for fever, chills, rigors, hypotension, nausea, or other signs and symptoms of CRS. If tolerated during C1D1, subsequent observation times can be reduced to 15 minutes.

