If a patient is taking any of the medications in the categories of strong CYP3A4 inhibitors and inducers, the investigator will assess and document the use of these medications known or suspected to fall in those categories. A sample list of cautionary medications that fall into the categories within this section can be found in Appendix Section 14.4. The lists of medications are not necessarily comprehensive. The investigator should consult the prescribing information when determining whether a concomitant medication can be safely administered with study treatment. Patients are prohibited from using strong CYP3A4 inhibitors in part B of the study, and as discussed in the inclusion/exclusion criteria, patients may need to wash out these medications before proceeding with part B of the study. In addition, the investigator should contact Subjects who, in the assessment by the investigator, require the use of any of the aforementioned treatments for clinical management should be removed from the trial. Subjects may receive other medications that the investigator deems to be medically necessary. The Exclusion Criteria describes other medications which are prohibited in this trial.

Mosunetuzumab: Given the expected pharmacology of mosunetuzumab, the transient release of cytokines (most resolved within the first 24 hours of the C1D1 dose) may suppress CYP450 enzymes and cause drug-drug interactions. Preliminary clinical data indicate that mosunetuzumab induced a transient elevation in plasma IL-6, with peak levels occurring in the majority of patients within 4-6 hours of the C1D1 dose, and returning to baseline by 24 hours. Patients may be of highest risk of a drug-drug interaction are those receiving concomitant medications that are CYP450 substrates and have a narrow therapeutic index (Appendix 14.4). Such concomitant medications should be monitored for

toxicity, and dose adjusted accordingly.

A sample list of cautionary medications that fall into the categories within this section can be found in Appendix Section 14.4. The lists of medications are not necessarily comprehensive. The investigator should consult the prescribing information when determining whether a concomitant medication can be safely administered with study treatment. In addition, the investigator should contact the principal investigator if questions arise regarding medications not listed above.

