4. Screening bone marrow biopsy and aspirate may be completed up to 12 weeks prior to study enrollment, and at time of CR (as close to date of CR as possible). Bone marrow biopsy may be waived at the discretion of the Principal Investigator.
5. See Section 7.1.4. Other procedures during screening are at the discretion of the treating investigator and may include standard-of-care assessments, central venous catheter placement, laboratory studies, or other measures.
6. The presence of archival tissue will be assessed during screening, and unstained slides may be collected. When available this tissue will be provided for central biobanking.
7. Baseline correlative blood draw (eg. For ctDNA measurements) may be done at any time prior to the C1D1 dose. Additional correlative timepoints will be collected at baseline, as well as around the time of any response assessment. Correlative blood draws should also be performed for the end of treatment or off study visit in patients who do not achieve CR at assessment. Additional timepoints may be drawn at the time of other expected blood draws at the discretion of the investigator.
8. See Table 8 for details of these tests.
- 9: End of treatment visit should be scheduled at the time of the expected cycle 9 day 1, or within 14 days of removal from protocol. Subjects who are not in CR and do not proceed with Cycle 9 Day 1 of polatuzumab vedotin and obinutuzumab as outlined in section 5.2 and 6.2.
10. Study-mandated visits are not required, but the study team may query records to assess disease status or vital status for up to 5 years after completion of therapy. Patients on alternative therapy should have AEs recorded for up to 30 days after last dose of study therapy or first administration of alternate therapy, whichever comes first.
11. Monitoring for tumor lysis syndrome should be performed on cycle 1 day 2. Liver function testing is optional. Additional supportive care and monitoring can be provided as determined by baseline testing and risk factors.

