7.1.2.3 Vital Signs

The investigator or qualified designee will take vital signs at screening, prior to the administration of each dose of trial treatment and at treatment discontinuation as specified in the Trial Flow Chart (Section 6.1). Vital signs should include temperature, pulse, respiratory rate, weight and blood pressure. Height is only required to be measured at screening only.

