a In laboratory TLS, two or more metabolic abnormalities must be present during the same 24-hour period within 3 days before the start of therapy or up to 7 days afterward. Clinical TLS requires the presence of laboratory TLS plus an increased creatinine level, seizures, cardiac dysrhythmia, or death.

b The corrected calcium level in milligrams per deciliter = measured calcium level in milligrams per deciliter +0.8x (4- albumin in grams per deciliter).

c Acute kidney injury is defined as an increase of 0.3 mg/dL (26.5 µmol/L) in creatinine level or a period of oliguria lasting 6 or more hours. By definition, if acute kidney injury is present, the patient has clinical TLS (Levin et al. 2007).

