14.8 Management Guidelines for Tumor Lysis Syndrome

Treatment for laboratory and/or clinical presentations of tumor lysis syndrome (TLS) will follow institutional practice. Prior to each treatment given during Cycles 1 and 2, the patient's serum chemistry and hematologic laboratory samples should be obtained and results reviewed and prophylactic measures considered according to the guidelines described below. Access to nephrology consultation with acute dialysis services must be available in the event of clinically significant TLS.

As mosunetuzumab has the potential for B-cell killing, the potential risk of TLS in all patients must be considered, along with the need for prophylaxis for TLS prior to the initiation of mosunetuzumab. Owing to the potential risk of TLS following administration of study treatment, patients must have a creatinine clearance ³40 mL/min to participate in this trial.

All patients should be considered for prophylaxis for TLS prior to mosunetuzumab administration during Cycles 1 and 2. Prophylaxis guidelines include the following:

- Hydration, consisting of a fluid intake of approximately 2-3 L/day starting 24-48 hours prior to the first dose of mosunetuzumab.

If a patient receives study treatment in the outpatient setting, fluid intake should be maintained at 2-3 L/day for at least 24 hours after mosunetuzumab administration.

Modification of fluid rate should be considered for individuals with specific medical needs.

- Administration of an agent to reduce uric acid:

Allopurinol (e.g., 300 mg/day orally beginning 72 hours prior to dose and continuing for 3-

7 days afterward) should be administered at the discretion of the investigator.

For patients with elevated uric acid levels prior to mosunetuzumab treatment or considered to be at high risk for TLS: rasburicase (e.g., 0.2 mg/kg IV over 30 minutes prior to first dose mosunetuzumab and daily for up to 5 days thereafter) should be administered, unless contraindicated (Elitek® [rasburicase] U.S. Package Insert).

Treatment with allopurinol/rasburicase should continue as specified above, or if laboratory evidence of TLS is observed until normalization of serum uric acid or other laboratory parameters.

If the above measures are contraindicated or are otherwise inappropriate in the view of the investigator, the Principal Investigator should be contacted for further guidance.

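### Part A schedules uric acid, phosphate and next-day TLS labs only around the 5 mg dose and none after the first 45 mg dose; separately, transient Grade 2 CRS may be missed between visits

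*Combined protocol and SAP*

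**What the plan says.** **Dosing.** Table 2 (Section 5.3) gives 5 mg on C1D1 and 45 mg on C1D8, C1D15 and day 1 of Cycles 2-8.

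**TLS laboratory schedule.** The Section 6.1 grid marks uric acid and phosphate at C1D1 and C1D2 only. Footnote 11 reads "Monitoring for tumor lysis syndrome should be performed on cycle 1 day 2" and goes on to allow further monitoring according to baseline tests and risk factors. The chemistry panel with LDH is marked at screening, C1D1, C1D2, C1D8, C1D15, day 1 of Cycles 2-8 and end of treatment. Table 8 lists potassium and calcium in that panel.

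**TLS definition and guidance.** For laboratory TLS, Table 15 footnote a (Appendix 14.7) requires that "two or more metabolic abnormalities must be present during the same 24-hour period within 3 days before the start of therapy". The same footnote extends this window to the seventh day after treatment begins. Appendix 14.8 says "All patients should be considered for prophylaxis for TLS prior to mosunetuzumab administration during Cycles 1 and 2". It also asks for chemistry before each treatment in those cycles, and for hospitalization in later cycles to be considered if clinical or laboratory TLS develops in Cycle 1. TLS is a mosunetuzumab adverse event of special interest (Section 7.2.1).

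**CRS.** Section 4.3.1 describes the regimen "with a shortened window of CRS associated mostly with only the first two doses of mosunetuzumab during cycle 1". Section 5.4.2 reports an IL-6 rise "with peak levels occurring in the majority of patients within 4-6 hours of the C1D1 dose". Section 5.3 sets at least 30 minutes of observation at C1D1 and adds "If tolerated during C1D1, subsequent observation times can be reduced to 15 minutes". Under Section 7.1.2.3 the investigator or designee "will take vital signs at screening, prior to the administration of each dose of trial treatment and at treatment discontinuation". The C1D2 column of the grid has chemistry, uric acid and phosphate, but no vital signs or AE review.

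**The concern.** The dedicated TLS checks sit around the smallest dose. The first full dose, nine times larger, has no next-day check, and the two analytes that chemistry does not supply are not drawn again in Part A. Appendix 14.8 nevertheless carries the TLS risk through Cycles 1 and 2 and attaches an action to laboratory TLS found in Cycle 1. Whether such an event is found after C1D8 then depends on what each investigator chooses to order, so the count of this event of special interest partly reflects local practice.

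CRS ascertainment is a separate matter, because TLS tests do not detect CRS. Grade 2 CRS turns on hypotension or hypoxia (Table 13). Footnote b of that table warns that corticosteroid premedication may blunt fever, and Section 5.3 gives corticosteroids before and at 24 and 48 hours after doses in Cycles 1 and 2. A patient at home with brief hypotension and little fever may have nothing that prompts a call, and questioning a week later cannot recover a blood pressure that nobody took. Grade 2 or higher CRS drives an accrual-suspension rule in Section 8.0.

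**Working it through.** **1. Step size and timing**
- Dose step: 45 / 5 = 9.
- C1D1 to the dedicated check at C1D2: 1 day.
- C1D8 to the next scheduled panel at C1D15: 15 − 8 = 7 days. With ±1 day on each visit, the range is 14 − 9 = 5 to 16 − 7 = 9 days.

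**2. What the scheduled labs can show**
- Table 15 has four laboratory analytes: uric acid, phosphate, potassium and calcium. Two or more must be abnormal, so there are 4 × 3 / 2 = 6 possible pairs.
- At C1D1 and C1D2 all four are scheduled: 6 of 6 pairs.
- From C1D8 on, only potassium and calcium are scheduled: 1 of 6 pairs.
- The C1D8 panel is drawn before the 45 mg dose (Appendix 14.8), so it cannot show that dose's effect.

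**3. The Table 15 window**
- If start of therapy means C1D1, the window closes at day 1 + 7 = day 8, the nominal day of the first 45 mg dose. With ±1 day on C1D8, it ends between 1 day after and 1 day before that dose. C1D15 lies 14 − 7 = 7 days beyond it.
- If the window restarts with the C1D8 dose, it closes on the nominal C1D15, so a panel drawn 5 to 9 days after the dose may fall inside or outside it.
- Appendix 14.8 acts on laboratory TLS at any time in Cycle 1, which lasts 21 days. The literal window does not cover most of that period.

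**4. The CRS rule**

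The plan's boundaries are 6/15, 9/30 and 11/42 against a 15% rate. A one-sided 95% Clopper-Pearson lower limit reproduces each as the smallest count whose limit exceeds 0.15:

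| n | Count below boundary: lower limit | Boundary: lower limit |
|---|---|---|
| 15 | 5: 0.142 | 6: 0.191 |
| 30 | 8: 0.140 | 9: 0.166 |
| 42 | 10: 0.135 | 11: 0.154 |

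The rule is sound on its own terms if events are captured. As an illustration only, suppose a share f of patients with Grade 2+ CRS is missed, so that the recorded rate is true rate × (1 − f), with looks at exactly 15, 30 and 42 patients. Chance of crossing the rule at some look:

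| True rate | f = 0 | f = 10% | f = 25% |
|---|---|---|---|
| 15% | 0.06 | 0.03 | 0.01 |
| 25% | 0.52 | 0.38 | 0.18 |
| 30% | 0.78 | 0.64 | 0.38 |

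The true rates and f are assumptions. The documents support no value of f, including any value above zero.

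**The case against.** The strongest defence is that this is a risk-adapted design. Footnote 11 and Appendix 14.8 allow further laboratory monitoring by judgment and institutional practice. Appendix 14.8 also suggests telemetry for high-risk patients, continues their prophylaxis with later doses and asks for chemistry before every Cycle 1-2 dose. The definition and the dedicated checks could both be deliberately anchored to the start of treatment. This defence stands in part: an investigator can close the gap for any patient. It does not make the count uniform across patients, and it does not explain why laboratory TLS anywhere in Cycle 1 leads to action when the dedicated tests stop at C1D2.

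Four stronger readings might be inferred, and the documents do not support them.
- *No TLS-relevant test follows a 45 mg dose.* Potassium and calcium are scheduled at C1D15 and on day 1 of Cycles 2-8.
- *The rasburicase guidance conflicts with the schedule.* Its trigger is a raised uric acid before mosunetuzumab treatment, with the example given before the first dose, and uric acid is scheduled at C1D1.
- *CRS between visits goes unseen, so the suspension count is biased low.* AEs are recorded continuously from consent, reviewed at C1D8 and C1D15, and elicited by asking about the time since the last visit. Nor does dividing 15 minutes by 4-6 hours (15/360 = 4% to 15/240 = 6%) measure missed CRS: an IL-6 peak is not CRS onset, and that timing is preliminary and concerns the C1D1 dose.
- *The panel omits creatinine.* It does not appear in Table 8 as read here, but the table was machine-read and any omission is probably clerical.

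**Conclusion.** The point holds in a limited form. The Section 6.1 grid and footnote 11 place uric acid, phosphate and the only next-day TLS check at C1D1-C1D2. After the ninefold step-up, the scheduled labs fall to 1 of 6 defining pairs, drawn about 7 days later, and the Table 15 window read literally closes at about the day of that step. Laboratory TLS after C1D8 can be missed, or measured and still fall outside the definition.

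The consequence lies in the count of this event of special interest and in AE frequency, which is an exploratory objective. TLS has no suspension rule of its own, and laboratory-only TLS at the stated minimum Grade 3 does not enter the Grade 4 non-hematologic rule. The CR endpoint is untouched.

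On CRS, the supportable statement is that transient Grade 2 events may be missed between the end of observation and the next visit with vital signs, and that any such loss would make the 6/15, 9/30, 11/42 rule less likely to trigger. Its size is unknown. Both conclusions rest on the machine-read grid being correct and on no extra tests or contacts being ordered.

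**What to change.** 1. **Section 6.1 grid:** add uric acid and phosphate to the C1D8 and C1D15 draws already scheduled. C1D8 then gives a full four-analyte value before the step-up, and C1D15 a full one about a week after it. This restores 6 of 6 pairs at those visits but would not catch a change that resolves within days. Cost: 2 analytes × 2 draws × 42 patients = at most 168 extra results, with no new visit.
2. **C1D2 visit:** add vital signs and AE review to this existing visit. Cost: a little more data collection, and somewhat more low-grade events on record.
3. **Reconcile on TLS:** footnote 11, the Section 6.1 grid, Appendix 14.8 and the Table 15 window should agree on whether and when TLS is checked after the first 45 mg dose, and on what start of therapy means in the window. Without the second, values from item 1 may not count. This review proposes no further check.
4. **Reconcile on CRS:** the observation times in Section 5.3 should be reconciled with the CRS and cytokine timing in Sections 4.3.1 and 5.4.2. This review proposes no duration.
5. **Check in the source:** whether Table 8 lists creatinine, which the kidney-injury criterion in Table 15 needs, and whether the footnote 11 marker belongs on the CBC cell for Cycles 2-8, where its text does not fit.

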6.2 Part B Study Flow Chart

Treatment Cycle/Title	Part B					
	Cycle 9 Day 1	Cycle 9 Day 2	Cycle 9 Day 8	Cycle 9 Day 15	Cycles 10-14 Day 1	
Scheduling Timing and Window			± 1 day	± 1 day	± 2 days	
Prior and Concomitant Medication Review	X		X	X	X	
Trial Treatment Administration	X		X	X	X	
Post-study disease status						
Survival Status						
Review Adverse Events ¹	X		X	X	X	
Physical Examination	X		X	X	X	
Vital Signs and Weight	X		X	X	X	
Height						
ECOG Performance Status	X		X	X	X	
CBC with Differential ⁵	X		X	X	X ¹¹	
Comprehensive Serum Chemistry Panel ⁵ and LDH	X	X ⁷	X	X	X	
Uric acid, Phosphate	X	X ⁷				
Tumor Imaging ²					X ²	
Bone Marrow Biopsy and Aspirate ³						
Correlative Studies Blood Collection ⁴	X					

Cycle length = 21 days

1. AE will be recorded from the time of a subject signing consent, up until off study visit.
2. A CT scan should be performed between cycle 11 day 1 and cycle 12 day 1 (as close to cycle 12 day 1 as possible). Post cycle 14 PET/CT (with concurrent diagnostic CT scan of the chest, abdomen, and pelvis (neck if clinically indicated)). Additional interim and surveillance scans can be performed at investigator discretion.
3. Screening bone marrow biopsy and aspirate may be completed up to 12 weeks prior to study enrollment, and at time of CR (if positive at enrollment or of not performed to date of CR as possible). Bone marrow requirements may be waived at the discretion of the Principal Investigator.
4. Baseline correlative blood draw (eg. For ctDNA measurements) should be done at any time prior to the C9D1 dose, preferably at the time other C9D1 labs have been collected. Additional timepoints will be collected with day 1 labs prior to cycle 10, 11, as well as around the time of any response assessment. Correlative blood draws should also be performed at the off study visit in patients who did not have a formal response assessment. Additional timepoints may be drawn at the time of other expected blood draws at the discretion of the investigator.
5. See Table 8 for details of these tests.
6. Study-mandated visits are not required, but the study team may query records to assess disease status or vital status for up to 5 years after completion of therapy. If a patient receives alternative therapy should have AEs recorded for up to 30 days after last dose of study therapy or first administration of alternate therapy, whichever comes first. 7. If a patient experiences lysis syndrome and proceed with Part B, additional lab monitoring and supportive care should be performed at the discretion of the investigator.

